### 3 OBJECTIVES AND ENDPOINTS

OBJECTIVES	ENDPOINTS	JUSTIFICATION FOR ENDPOINTS
Primary		
To evaluate the effect of an 8-week flavokavain A/B-free kava trial in GAD patients on biomarker and anxiety scale changes, and the relationships between these measures, in a double-blind RCT.	
 
Plasma changes in PRKACA, cortisol, urinary TCE, and urinary NA-5HT and cortisol levels
 
Changes in HAM-A score pre to post treatment
 
	
 
Biomarkers of interest
 
Measure of anxiolysis
 

Compliance		
	
 
Liver function tests
 
Number of missed doses
 
	
 
Standard measures of liver function
 
Quantified measure of compliance
 

Tertiary/Exploratory		
N/A	N/A	N/A

## 4 STUDY DESIGN

### 4.1 OVERALL DESIGN

**Aim:** To validate PRKACA reduction (primary outcome), cortisol, urinary TCE, and NA-5HT reductions (secondary outcomes) as biomarkers for kava-induced anxiolysis in GAD.

**Study design:** We will recruit and screen potential participants until we are able to randomize and enroll 26 individuals with GAD, with the expectation that 20 will complete the study (10 per arm) based on a conservative estimate of a 25% drop-out rate (the drop-out rate for our pilot study was 19%). We will build on our prior work with smokers by evaluating the utility of PRKACA as a biomarker for kava-induced anxiolysis among individuals with GAD. A one week double-blinded randomized, parallel, placebo-controlled trial of kava in GAD patients will be conducted. To minimize the risk of adverse events, particularly liver dysfunction, we will use flavokavain A/B-free kava in this study. Participants will be randomized, stratified by sex, to one of two conditions—placebo dosed three times a day or 75 mg of kava dosed three times a day. All pills will be taken with meals. Potential adverse effects will be evaluated via serum liver biochemistries and assessment of clinical symptoms in all participants at baseline, post treatment (day 7) and every 4 weeks for 12 weeks following discontinuation of treatment. Blood and urine for biomarker assessments will be collected at baseline and post treatment (day 7). CYP2D6 testing will be conducted at the screening visit to examine, at the end of the study, whether kava metabolism through this enzyme affects the biomarker responses.

### 4.2 SCIENTIFIC RATIONALE FOR STUDY DESIGN

Exploring the potential of plasma PRKACA, and in an exploratory fashion of cortisol, urinary TCE and NA-5HT, as surrogate biomarkers of kava's anxiolytic potential.

### 4.3 JUSTIFICATION FOR DOSE

We have isolated the major chemicals in kava and determined their benefits (66) and risks (32) in vivo. With such knowledge, we screened twenty-five commercially available kava products and quantified the major beneficial kavalactones, including kavain, dihydrokavain, methysticin, and dihydromethysticin (DHM, the chemopreventive ingredient), and the hepatotoxic compounds – flavokavains A and B (30). We identified one dietary kava product from Gaia Herbs (Kava Root) for our pilot human trial that has a high DHM content and low flavokavain A and B content. To ensure consistency, we characterized the content of three batches of this product by HPLC and NMR. Each capsule contained  $75 \pm 3$  mg of kavalactones (the anxiolytic ingredients), consistent with the labeled 75 mg kavalactone per capsule. Each capsule also contained ~20 mg DHM. With three capsules per day, the human daily dose of kava is within the proposed anxiolytic range (120-280 mg daily (14)); the amount of DHM would be comparable

to its in vivo chemopreventive dose. This kava product also contained minimal flavokavains A and B (<1.0 mg/capsule).

#### 4.4 END OF STUDY DEFINITION

The study will come to an end when the data for 13 controls and 13 subjects with GAD has been collected and analyzed.

## 5 STUDY POPULATION

### 5.1 INCLUSION CRITERIA

**1)** Adults ages 18-50 who meet DSM-5 criteria for GAD as the primary psychiatric diagnosis. **2)** No more than one failed therapeutic trial of an FDA approved medication for the treatment of GAD. **3)** Score of >14 on the Hamilton Anxiety Rating Scale at screening. **4)** At least a 4 (moderate) on the Clinical Global Impressions Severity Scale at screening. **5)** Females of potential childbearing status must use adequate contraceptive precautions.

### 5.2 EXCLUSION CRITERIA

**1)** Any change in current SSRI, SNRI, or other non-benzo anxiolytic medication within 6 weeks of baseline visit. **2)** Inability to refrain from acetaminophen, alcohol or other potentially hepatotoxic substances. **3)** History of liver disease or current liver disease or clinically significant elevation in serum liver chemistries. **4)** Unstable medical or neurological condition. **5)** Positive urine drug screen for substances of abuse. **6)** Active substance abuse/dependence. **7)** Lifetime history of a psychotic disorder, bipolar disorder, PTSD or OCD. **8)** Any significant risk for self-harm or suicidality as determined by the principal investigator or suicide attempt within the last 6 months. **9)** Psychotherapy newly instituted during the 6 weeks leading up to enrollment in the study. Subjects established in psychotherapy without change during the course of the study may participate. **10)** Montgomery-Asberg Depression Rating Scale (MADRS) > 20 (moderate or severe depressive symptoms).

### 5.3 LIFESTYLE CONSIDERATIONS

This study will exclude any individual who is a current tobacco smoker and anyone who is not able to abstain from alcohol consumption for the duration of the study.

### 5.4 SCREEN FAILURES

Subjects who do not meet inclusion and/or meets criteria for any of the exclusion criteria will be deemed a screen fail.

### 5.5 STRATEGIES FOR RECRUITMENT AND RETENTION

Subjects will be recruited from the population of patients seen in clinics staffed by the UF Department of Psychiatry, through advertisements and referrals in the community. These advertisements will be in the form of flyers and newspaper ads. When study referrals are received, a member of the research team will make contact within 24 hours to conduct a pre-screening phone interview. The study will be described to the potential participant and a brief set of questions will be asked to determine eligibility in the trial. Those who meet the inclusion/exclusion criteria below and are interested in participation will then be scheduled for an in-person screening visit. At that screening visit the informed consent will be reviewed in detail and the participant will be given the opportunity to ask questions prior to signing. Participants who are eligible at both screening and baseline will be randomized to receive study drug

and given instructions on taking it. At the end of this visit the participant will be scheduled for the next study visit.

Compliance will be insured via the following methods:

- Close monitoring during participation
- Weekly reminder phone calls to confirm study visits
- 24/7 access to study coordinator and study doctor during participation
- Establishing appropriate rapport such that the participant feels cared about by the research team and is motivated to return.
- Providing ease of access to the research facilities—participants will be given parking or bus vouchers to facilitate their visits. Visits will be scheduled to accommodate the participants' schedules as much as possible within the limitations of the study parameters.

Participants will be compensated \$25 for each assessment visit, and for the long term follow-up visits. Money will be loaded onto a prepaid visa card remotely, and will be provided at two time points 1) the end of the treatment (or at the time that the participant drops out) and 2) at the end of the 12 week follow up. Providing compensation at these delayed time points rather than after every visit encourages participation in the assessment visits. Note that participants are not compensated for participating in treatment, rather they are compensated for participating in the research assessments.

## 6 STUDY INTERVENTION

### 6.1 STUDY INTERVENTION(S) ADMINISTRATION

#### 6.1.1 STUDY INTERVENTION DESCRIPTION

Bottles of flavokavain AB-free kava (75 mg kavalactones/capsule) with the same lot number will be directly purchased from Thorne Research Inc. This product will be used because of its lack of flavokavains A and B (<0.2 mg/capsule) and consistent content of total kavalactones. Participants will take either one 75 mg capsule of kava or one placebo capsule three times a day for one week.

#### 6.1.2 DOSING AND ADMINISTRATION

Optimal dosing regimen to be determined in phase 1 (75 mg three times a day or 225 mg once a day).

A trained study team member will retrieve the study supplements from IDS Pharmacy and deliver them to the participant at the UF Health Outpatient Psychiatry Clinic. Instructions will be provided in writing on supplement administration and storage of supplements. Participants will be asked to keep track of any missed doses. Unused supplements will be returned to IDS via the study personnel at the end of the trial and will be destroyed by IDS.

### 6.2 PREPARATION/HANDLING/STORAGE/ACCOUNTABILITY

#### 6.2.1 ACQUISITION AND ACCOUNTABILITY

Participants will be randomized to receive kava or placebo and given bottles with the correct number of pills and instructions on how to take the medication.

#### 6.2.2 FORMULATION, APPEARANCE, PACKAGING, AND LABELING

Bottles of flavokavain AB-free kava (75 mg kavalactones/capsule) with the same lot number will be directly purchased from Thorne Research Inc. This product will be used because of its lack of flavokavains A and B (<0.2 mg/capsule) and consistent content of total kavalactones. For ongoing quality control, three capsules from each bottle will be analyzed via our established method to ensure adequate and constant content of total kavalactones and no flavokavains A and B. The Investigational Drug Service (IDS) pharmacy will package the investigational kava. Supplies with the appropriate number of capsules for each subject will be prepared and bottled for administration.

---

### 6.2.3 PRODUCT STORAGE AND STABILITY

Product will be stored according to manufacturer recommendations. All unused supplement will be returned to IDS via study personnel and destroyed by IDS.

---

### 6.2.4 PREPARATION

Bottles of flavokavain AB-free kava (75 mg kavalactones/capsule) with the same lot number will be directly purchased from Thorne Research Inc. This product will be used because of its lack of flavokavains A and B (<0.2 mg/capsule) and consistent content of total kavalactones.

### 6.3 MEASURES TO MINIMIZE BIAS: RANDOMIZATION AND BLINDING

Eligible study participants will be randomly assigned to one of two groups: kava supplement or placebo. The pharmacist will use a computerized program SAS PROC PLAN procedure to generate the randomization scheme. Sequentially numbered, sealed, opaque envelopes containing group assignment (kava supplement or placebo) will be prepared by the pharmacist and numbered for each group 1 to 20. When a participant meets criteria to be randomized the study coordinator will open the next (sequentially numbered) appropriate envelope for participant assignment. Because this is a double-blinded study, neither the investigators nor the participants will know whether participants have received the kava supplement or placebo. The placebo supplement will be provided by identical capsules that contain methylcellulose, an inactive ingredient. The pharmacist will distribute identical capsules (kava and placebo); thus, no distinguishing characteristics will be present. The list of prepared supplements will be maintained by the pharmacist who will distribute the appropriate supplements for the next consented, eligible study participant.

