### 9.2 SAMPLE SIZE DETERMINATION

We will recruit and screen potential participants until we are able to randomize and enroll 26 individuals with GAD, with the expectation that 20 will complete the study (10 per arm) based on a 75% success rate (the retention rate for our pilot study was 81%). Of particular interest is determining the utility of measuring changes in PRKACA as a marker of kava-induced anxiolysis. To provide context, the effect size seen in our pilot work was .794 (Cohen's  $f$ ) for PRKACA reductions on kava from baseline. Based on the proposed design, with 10 subjects per arm, we have 0.80 power to detect an effect size (Cohen's  $f$ ) of 0.73 (82, 83). While this represents a large effect size, it is consistent with what was found in our pilot work.

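### Section 6.3 puts the arm name in envelopes that the coordinator opens, numbers them in a way that literally gives one series per arm, and leaves out sex stratification and the total of 26

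*Combined protocol and SAP*

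**What the plan says.** Section 6.3 (Randomization and Blinding) states that "Eligible study participants will be randomly assigned to one of two groups: kava supplement or placebo". The pharmacist generates the scheme with SAS PROC PLAN and prepares "Sequentially numbered, sealed, opaque envelopes containing group assignment (kava supplement or placebo"), which are "numbered for each group 1 to 20". When a participant qualifies, "the study coordinator will open the next (sequentially numbered) appropriate envelope for participant assignment". The section then says that investigators and participants will not know the treatment, that capsules are identical, and that the pharmacist keeps the list of prepared supplements and dispenses them. It gives no strata, block size or allocation ratio, and does not say what makes an envelope appropriate.

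Section 4.1 (Overall Design) adds a feature that 6.3 lacks: "Participants will be randomized, stratified by sex, to one of two conditions". Section 9.2 (Sample Size Determination) recruits "until we are able to randomize and enroll 26 individuals with GAD" and expects 20 to complete, 10 per arm. Section 2.3.3 gives the study coordinator the task of coordinating screening, and section 5.5 makes the coordinator available to participants around the clock.

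**The concern.** Two protections are at stake.

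- **Concealment.** Whoever decides that a candidate is eligible must not know, or be able to guess, the next assignment. Separate numbered series for each arm would remove that protection, however opaque the envelopes are.
- **Blinding.** An envelope that states the arm shows it to whoever opens it. Here that is a person involved in screening the next candidate and in regular contact with participants already enrolled. Section 3 lists change in HAM-A, a rating scale, among the primary endpoints, so knowledge of the arm within the study team matters. With about 10 completers per arm, a few foreseeable assignments could shift the comparison.

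There is also a practical matter. A scheme that does not mention its stratification factor, and whose count does not match the number randomised, cannot be carried out or audited from the text alone.

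**Working it through.** **Inputs from the documents**

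- Envelopes: 1 to 20 for each group (6.3).
- Groups as defined in 6.3: kava and placebo.
- Content of envelope: arm assignment. Opened by: the coordinator (6.3).
- To be randomised: 26. Expected completers: 20 (4.1, 9.2). Dropout: 25% (4.1).
- Stratification: sex (4.1). Sex mix: not given; the synopsis sets no restriction on gender.

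**Step 1. The plan's own figure.** 20 / (1 − 0.25) = 26.7, and 26 × 0.75 = 19.5 completers. The stated 26 therefore reproduces to within one participant. It is the number the envelopes must serve. The 20 in 6.3 equals the completer target, but no section says where it comes from.

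**Step 2. What each meaning of group gives**

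| Meaning of group in 6.3 | Envelopes | Against 26 randomised | Concealment before opening |
|---|---|---|---|
| Treatment arm (the section's own use) | 2 × 20 = 40 | Enough: 13 needed per arm at equal allocation | Lost: each series holds a single assignment |
| Sex stratum (fits 4.1 and the word *appropriate*) | 2 × 20 = 40 | Enough unless one sex supplies 21 or more | Possible, if arms are mixed within each series |

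Under the arm reading, unmarked envelopes would not help for long. The first opening from a series would show what the rest of it contains.

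**Step 3. Chance that 20 per sex runs out.** Let X be the number of one sex among 26, with X ~ Binomial(26, p), where p is that sex's assumed share. A stratum runs out if X ≥ 21 or X ≤ 5:

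P = P(X ≥ 21) + P(X ≤ 5)

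| Assumed share p | P(one sex exceeds 20) |
|---|---|
| 0.50 | 0.0025 (0.2%) |
| 0.60 | 0.021 (2.1%) |
| 0.67 | 0.096 (9.6%) |
| 0.70 | 0.163 (16.3%) |
| 0.75 | 0.337 (33.7%) |
| 0.80 | 0.577 (57.7%) |

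The threshold of 20 is 20/26 = 77% of the trial. Only 26 numbers per sex would cover every possible split.

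**Step 4. Disclosure at opening.** This needs no arithmetic and does not depend on the meaning of group. The envelope holds the arm and the coordinator opens it. The blinding sentence in 6.3 names investigators and participants but not the coordinator, and no section separates the coordinator from screening or participant contact. Since the pharmacist keeps the supplement list and dispenses, the coordinator needs only a number, not the arm.

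**The case against.** The strongest defence is that arm-specific series would make the rest of 6.3 pointless. A PROC PLAN scheme and sealed, opaque, sequentially numbered envelopes have no purpose if the coordinator must know the arm in order to pick an envelope. The sponsor may well have meant two series, one per sex, which would explain both the phrase *for each group* and the choice of an appropriate envelope. This stands in part: the concealment failure follows from the literal wording and is not a stated procedure. Against the defence, 6.3 uses *group* for the arms in its other uses and never mentions sex.

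A reader might infer that 20 envelopes leave six of the 26 without an assignment. The documents do not support that. It requires a single list of 20 and ignores *for each group*. On the sex reading, 40 envelopes exist and a shortage is only possible. If a series did run out, the pharmacist, who holds the scheme, could extend it.

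A reader might also infer that the lists are unblocked and that imbalance within sex can be calculated. Section 6.3 is silent on blocking, and silence does not show that there is none.

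None of these arguments answers the disclosure of the arm name to the coordinator.

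**Conclusion.** The point holds, at the level of something the sponsor should correct. Its parts differ in certainty:

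- **Certain from the text:** the envelope discloses the arm to the coordinator, who also coordinates screening; 6.3 omits the sex stratification of 4.1; and 20 is not reconciled with 26.
- **Inferred:** one series per arm, with allocation known before opening. This is the literal meaning of 6.3, but no section says that envelopes are marked by arm, so it cannot be asserted that concealment is broken in practice.
- **Conditional:** if group means sex stratum, the chance of running out is 0.2% at an even mix, about 10% at 67% and 34% at 75%. This assumes a constant share and independent participants. The documents give no expected mix, so these figures show sensitivity and are not a forecast.

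The loss of concealment and blinding has no numerical size that the documents would allow one to compute.

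**What to change.** Rewrite the envelope procedure in 6.3 to state that:

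1. The pharmacist generates one sequential list per sex, with both arms mixed within it, by restricted randomisation such as permuted blocks. The block design is the trial statistician's choice, and the block size is held by the pharmacist.
2. Each list has enough numbers for any split of the 26. The simplest choice is 26 per sex, 52 in all.
3. The appropriate envelope is the next unopened one in the participant's sex stratum.
4. The envelope carries only a coded kit number, and the pharmacist alone holds the key from kit number to arm.

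The Version 7 rationale shows that screening had already begun, so the study file should also record how any envelopes already used were numbered and chosen.

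The cost is one revised PROC PLAN run, a new set of envelopes and a few sentences in 6.3. Sample size, visits and analysis are unaffected. If this is already the practice, only the text needs to change.

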The study coordinator for the proposed project has 6 years of experience and will be trained in all study procedures. She will coordinate the screening of potential participants and will meet with [name] weekly to discuss study progress. [name], a gastroenterologist with expertise in hepatology and liver transplantation, will be responsible for overseeing the medical safety monitoring for this trial. He has extensive experience as a medical monitor for national clinical trials of multiple medications. He will communicate with [name] on a regular basis, and will also communicate any and all adverse events to the data safety monitoring board. He will interpret the results of the liver biochemistries (all results will be blinded to treatment condition) and will be responsible for referring participants to appropriate additional clinical evaluation and intervention if needed.

Effective screening will rule out active medical or psychiatric conditions, including supplement or medication use, chronic alcohol use, and evidence of pre-existing liver disease that may prevent someone from participating in the studies. Once the subject enters the study, an experienced research team will closely follow him or her. The research team has developed considerable expertise in monitoring the safety of subjects participating in research studies. An experienced research psychiatrist and the hepatologist is available 24 hours a day, 7 days a week. If at any point in the procedures symptoms become distressing or dangerous, subjects will be withdrawn from the study and, if necessary, treatment instituted.

This project will be conducted in compliance with research statutes outlined in the Health Insurance Portability and Accountability Act. Each participant will be assigned a unique identification number, and this number will be used to link all subsequent information collected. This file will be secured with password access, since it represents a direct link between the name and identification number of a participant. All paper files and data are kept in locked file cabinets to ensure confidentiality. The other procedures to ensure confidentiality follow the regulations and policies of the University of Florida and UF Health. Data file archival and back-up will be performed on a regular basis. The routine monitoring, maintenance, and quality control of the databases will be the responsibility of [name].

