*Participant distress during evaluations:* All evaluations have been designed to minimize burden on patients with respect to fatigue, stress and/or discomfort. Only trained individuals will administer study tests and questionnaires. These individuals will be trained to be sensitive to signs of patient fatigue, stress or discomfort. Breaks during testing will be scheduled, and can be initiated by the patient if they desire. Participants may choose whether or not to receive the results of their clinical interviews. Participants who are assessed as suffering from an untreated psychiatric disorder and choose to obtain the results of their interview will be offered referrals to treatment locally if they choose. Participants will be free to discontinue their participation at any time if they feel that it is causing unacceptable distress or discomfort.

*Loss of Confidentiality:* All research material will be treated in a confidential manner, and only research staff will have access to the data. Confidentiality will be maintained by assigning identification numbers for all aspects of the project; all data entered into computer databases will use only this identifier. Data are kept in separate coded REDCap data sets and in locked cabinets in locked rooms at UF with access limited to a small number of study personnel. All clinical and other records have identifying names of participants and relatives removed. Electronic data will be password protected and stored in a database on a secure server that is also password protected, with no patient identifying information. No identifiable individual data are presented in scientific publications. Only research personnel will have access to this data.

*Risks of Treatments of Unknown Efficacy:* Participants will be informed by the investigators and through the written consent that few studies exist for kava treatment, and kava for GAD in particular has not been adequately tested.

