### 7.2 PARTICIPANT DISCONTINUATION/WITHDRAWAL FROM THE STUDY

Study subjects will be informed that they are welcome to withdrawal or discontinue the study at any time should they feel this is not their best interest, does not meet their time availability, or for any other reason they see fit. Subjects will be asked to speak with the study coordinator or the investigator to indicate their request for withdrawal and all study related activity will stop.

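### Section 6.3 has the study coordinator open envelopes that state the arm, so the coordinator learns all 26 assignments, and nothing separates that role from the Week 1 HAM-A rating

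*Combined protocol and SAP*

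**What the plan says.** Section 6.3 gives the pharmacist the job of generating the scheme: "The pharmacist will use a computerized program SAS PROC PLAN procedure to generate the randomization scheme". On what the envelopes hold, it says: "Sequentially numbered, sealed, opaque envelopes containing group assignment (kava supplement or placebo) will be prepared by the pharmacist". At each randomisation "the study coordinator will open the next (sequentially numbered) appropriate envelope for participant assignment". It then calls the study double-blind and explains that "neither the investigators nor the participants will know whether participants have received the kava supplement or placebo". The section closes with the pharmacist keeping the list of prepared supplements and handing out identical capsules.

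On the coordinator's role, section 2.3.3 states: "The study coordinator for the proposed project has 6 years of experience and will be trained in all study procedures". That section also has the coordinator run screening and attend weekly progress meetings. Section 5.5 promises participants "24/7 access to study coordinator and study doctor during participation". Under section 7.2, "Subjects will be asked to speak with the study coordinator or the investigator to indicate their request for withdrawal".

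On who rates, the only condition found is in section 2.3.3: "Only trained individuals will administer study tests and questionnaires". No role is named there and blinding is not required.

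**The concern.** The envelope holds the arm rather than a code, so whoever opens it is unblinded. Section 6.3 can be read in two ways, and both need repair. If the coordinator counts among the investigators, the section contradicts itself. If not, the trial has an unblinded, participant-facing role that is neither declared nor walled off. An unblinded coordinator can be acceptable, but the plan must say so and keep that person away from rating.

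What is at stake is mainly HAM-A. Section 3 lists its pre-to-post change under the primary objective and gives it as the measure of anxiolysis. Section 4.1 sets the aim of validating biomarkers against that anxiolysis. A Week 1 score given by someone who knows the arm, or who has heard it from the coordinator, could be shifted by that knowledge. Self-reported missed doses (section 6.4) and retention are exposed more weakly.

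**Working it through.** **Inputs**
- Randomised: 26; expected completers: 20, 10 per arm (section 9.2); planned drop-out 25% (section 4.1).
- HAM-A schedule: phone screen and Week 1 (section 1.3).
- Modelled outcomes: PRKACA, cortisol, urinary TCE and NA-5HT (section 9.4.1).
- HAM-A hypothesis: a correlation with PRKACA reduction of at least 0.3 within the placebo group (section 9.1).

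**The plan's own figure.** 20 / (1 − 0.25) = 26.7, which rounds up to 27; the plan has 26. In the other direction, 26 × 0.75 = 19.5, about 20 completers. The stated 26 is close enough to use.

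**Disclosure.** One envelope is opened per randomisation, so 26 × 1 = 26 of 26 assignments are shown to the coordinator. With a code in place of the arm the count would be 0 of 26.

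**HAM-A change scores.** Change = Week 1 score − screening score. The screening score precedes randomisation and the Week 1 score follows it. Hence 10 + 10 = 20 of 20 expected change scores contain a rating made after disclosure. This is the number open to influence. It does not show that any was influenced.

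**Modelled outcomes.** All four are laboratory measurements, so 0 of 4 is rater-scored.

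**The placebo-arm correlation.** With about 10 placebo completers, let X be PRKACA reduction and Y be HAM-A reduction. If a rater shifts every placebo score by the same amount c, then corr(X, Y + c) = corr(X, Y) and nothing changes. Only uneven rating error could move it.

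**If the arms were compared on HAM-A.** Section 9 specifies no such test, and the documents give no figure for rater error. As an illustration only, assume no true effect, a shift of b standard deviations between arms, 10 per arm and a two-sided 0.05 t test. The noncentrality is b × √(10/2) = 2.236b on 18 degrees of freedom.

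| Assumed shift b (SD) | False-positive rate |
|---|---|
| 0 | 5% |
| 0.2 | 7% |
| 0.4 | 14% |
| 0.6 | 25% |
| 0.8 | 40% |

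**Other safeguards in the plan.** Section 2.3.3 has liver biochemistry interpreted blind to treatment, and section 10.1.7 keeps monitoring reports aggregate. No matching statement covers the HAM-A rater.

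**The case against.** The strongest reply is that section 6.3 already contains a pharmacist-controlled route. Its last sentence has the pharmacist hold the list and distribute supplements, and sections 6.1.2 and 6.2.2 add pharmacy bottling and collection by a team member. On that route the coordinator never needs the arm, and identical capsules protect the participant's blind. This is a fair reading of the intent. It does not undo an opened envelope, however, and the section does not say how the envelope and the pharmacist's list connect. It also means that the disclosure serves no evident purpose.

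Second, nothing says that the coordinator rates HAM-A. The training sentence in section 2.3.3 concerns participant distress and is not a rater specification, and the same section lists data collectors and research assistants as well as the coordinator. This stands: the link to rating is an absence of any bar, not a stated duty.

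Third, the consequences are narrow. PRKACA is the named primary outcome (sections 2.1 and 4.1), and the synopsis endpoints omit HAM-A. Blinded participants track their own missed doses, and the DHM assay gives an objective check in the kava arm. Withdrawal requests may go to the investigator instead, and section 8.3.4 assigns adverse-event enquiry to the investigator. These points reduce the exposure, but HAM-A change remains a listed endpoint.

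Finally, the copy reviewed lacks some pages, including the text between sections 10.1.4 and 10.1.6. A statement of roles there could not be checked.

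**Conclusion.** The concern holds and should be fixed. Confidence is high that section 6.3, followed as written, shows all 26 assignments to a participant-facing role in a trial described as double-blind. It is equally clear that the text reviewed neither declares that role unblinded nor separates it from outcome rating. The 26 of 26 assumes that the coordinator opens every envelope, as the section describes. The 20 of 20 change scores assume the planned completion.

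The effect on the results is not shown and no size of bias is claimed. The four modelled biomarkers have little exposure through rating, and a uniform rating shift leaves the placebo-arm correlation unchanged. What remains is an avoidable, unguarded risk to HAM-A, the trial's only listed measure of anxiolysis.

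**What to change.** Amend section 6.3 so that the coordinator sends the participant's ID and sex to the pharmacist. The pharmacist alone consults the sex-stratified list and releases a bottle labelled only with the participant number, which a team member delivers as section 6.1.2 describes. Alternatively, keep the envelopes but put only a kit code inside. Either way, state how the assignment leads to the bottle, and name the coordinator, the delivering team member and the HAM-A raters among those kept blinded. The same amendment should say whether the envelope numbering of 1 to 20 for each group refers to sex strata or to arms. If it refers to arms, the series itself would reveal the allocation before opening.

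For participants already randomised, record whose assignment was disclosed and to whom, and report whether any unblinded person rated HAM-A at Week 1.

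The cost is one short amendment, which needs IRB approval before use (Statement of Compliance). No new role is needed, because the pharmacist already generates the scheme, prepares the envelopes and distributes the capsules. Screening was under way by version 7, and the documents do not say how many of the 26 had been randomised. The change protects only later participants; for earlier ones, disclosure can only be documented.
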